9.3.1.1. Suspected Unexpected Serious Adverse Reactions

Suspected unexpected serious adverse reactions (SUSARs) are serious events that are not listed in the IB and that the investigator reports as related to investigational product or procedure. Lilly has procedures that will be followed for the recording and expedited reporting of SUSARs that are consistent with global regulations and the associated detailed guidances.

9.3.1.2. Adverse Event Monitoring with a Systematic Questionnaire

Before administering the Nasal and Non-nasal Score Questionnaire (see [Appendix 6](#) for a copy of the questionnaire) and Edinburgh Hypoglycemia Scale (see [Appendix 7](#)), study site personnel will question the patient about any change in the preexisting condition(s) and the occurrence and nature of any AEs. Study site personnel will explain the possibility to the patient of AEs associated with the study and that these AEs will be captured during the study through the use of the Nasal and Non-nasal Score Questionnaire and Edinburgh Hypoglycemia Scale.

Nonserious AEs obtained through the questionnaire are recorded and analyzed separately.

Only SAEs elicited through the Nasal and Non-nasal Score Questionnaire and Edinburgh Hypoglycemia Scale are to be recorded as AEs via electronic data entry and reported to Lilly or its designee within 24 hours as SAEs.

9.3.2. Complaint Handling

Lilly collects product complaints on investigational products and drug delivery systems used in clinical trials in order to ensure the safety of study participants, monitor quality, and to facilitate process and product improvements.

Patients should be instructed to contact the investigator as soon as possible if he or she has a complaint or problem with the investigational product (or drug delivery system) so that the situation can be assessed.

9.4. Treatment of Overdose

Not applicable.

9.5. Safety

9.5.1. Laboratory Tests

For each patient, laboratory tests detailed in [Appendix 2](#) should be conducted according to the Schedule of Activities (Section 2).

Lilly or its designee will provide the investigator with the results of laboratory tests analyzed by a central vendor, if a central vendor is used for the study.

9.5.2. Vital Signs

For each patient, vital sign measurements should be conducted according to the Schedule of Activities (Section 2), and following the study-specific recommendations included in the Manual of Operations for the study.

Blood pressure and pulse rate should be measured after at least 5 minutes supine.

If orthostatic measurements are required, patients should be supine for at least 5 minutes and stand for at least 2 minutes.

If the patient feels unable to stand, supine vital signs only will be recorded.

Unscheduled orthostatic vital signs should be assessed, if possible, during any AE of dizziness or posture-induced symptoms. Additional vital signs may be measured during each study period if warranted.

9.5.3. Electrocardiograms

For each patient, ECGs should be collected according to the Schedule of Activities (Section 2) and the study-specific recommendations included in Manual of Operations for the study.

Any clinically significant findings from ECGs that result in a diagnosis and that occur after the patient receives the first dose of the investigational product should be reported to Lilly, or its designee, as an AE via electronic data entry.

For each patient, a single 12-lead digital ECG will be collected according to the Schedule of Activities (Section 2). Electrocardiograms must be recorded before collecting any blood samples. Patients must be supine for approximately 5 to 10 minutes before ECG collection and remain supine but awake during ECG collection. Electrocardiograms may be obtained at additional times, when deemed clinically necessary. All ECGs recorded should be stored at the investigational site.

Electrocardiograms will be interpreted by a qualified physician (the investigator or qualified designee) at the site as soon after the time of ECG collection as possible, and ideally while the patient is still present, to determine whether the patient meets entry criteria at the relevant visit(s) and for immediate patient management, should any clinically relevant findings be identified.

If a clinically significant finding is identified (including, but not limited to, changes in QT/QTc interval from baseline) after enrollment, the investigator will determine if the patient can continue in the study. The investigator, or qualified designee, is responsible for determining if any change in patient management is needed, and must document his/her review of the ECG printed at the time of collection. Any new clinically relevant finding should be reported as an AE.

9.5.4. Other Tests

Blood samples will be collected as specified in the Schedule of Activities (Section 2) and stored for future exploratory analyses, which may include an assessment of anti-glucagon antibodies. Should immunogenicity be assessed, it will be done using a validated assay designed to detect antidrug antibodies in the presence of LY900018. Antibodies may be further characterized and/or evaluated for their ability to neutralize the activity of the LY900018.

Samples will be retained for a maximum of 15 years after the last subject visit, or, for a shorter period, if local regulations and ethical review boards (ERBs) allow, at a facility selected by the sponsor. The duration allows the sponsor to respond to future regulatory requests related to LY900018. Any samples remaining after 15 years will be destroyed.

A nasal and injection-site inspection will be conducted in advance of the hypoglycemic induction procedure. This inspection will ascertain whether either sites are normal in appearance prior to drug administration. The nasal and injection-site inspection will also be done 90 minutes following glucagon administration.

9.5.5. Safety Monitoring

The Lilly clinical pharmacologist or CRP/scientist will monitor safety data throughout the course of the study.

Lilly will review SAEs within time frames mandated by company procedures. The Lilly clinical pharmacologist or CRP will periodically review the following data:

- trends in safety data
- laboratory analytes including HbA1c and electrolytes (see [Appendix 2](#))
- adverse events including monitoring of nasal cavity and injection site.

When appropriate, the Lilly clinical pharmacologist or CRP will consult with the functionally independent Global Patient Safety therapeutic area physician or clinical research scientist.

9.5.5.1. Hepatic Safety

If a study patient experiences elevated alanine aminotransferase (ALT) $\geq 3X$ upper limit of normal (ULN), alkaline phosphatase (ALP) $\geq 2X$ ULN, or elevated total bilirubin $\geq 2X$ ULN, liver tests ([Appendix 4](#)) should be repeated within 3 to 5 days including ALT, aspartate aminotransferase, ALP, total bilirubin (TBL), direct bilirubin, gamma-glutamyl transferase, and creatinine kinase to confirm the abnormality and to determine if it is increasing or decreasing. If the abnormality persists or worsens, clinical and laboratory monitoring should be initiated by the investigator based on consultation with the Lilly clinical pharmacologist or CRP. Monitoring should continue until levels normalize and/or are returning to approximate baseline levels.

Additional safety data should be collected if 1 or more of the following conditions occur:

- elevation of serum ALT to $\geq [5X]$ ULN on 2 or more consecutive blood tests
- elevated serum TBL to $\geq [2X]$ ULN (except for cases of known Gilbert's syndrome)
- elevation of serum ALP to $\geq [2X]$ ULN on 2 or more consecutive blood tests
- patient/subject discontinued from treatment due to a hepatic event or abnormality of liver tests
- hepatic event considered to be an SAE.

9.6. Pharmacokinetics

At the visits and times specified in the Schedule of Activities (see [Section 2](#)), venous blood samples of approximately 4 mL each will be collected to determine the plasma concentrations of glucagon and DPC. Three samples may be collected per subject at additional time points during the study if warranted and agreed upon between both the investigator and sponsor. DPC samples are collected from patients treated with NG only. Instructions for the collection and handling of blood samples will be provided by the sponsor. The actual date and time (24-hour clock) of each sampling will be recorded.

9.6.1. Bioanalysis

Samples will be analyzed at a laboratory approved by the sponsor and stored at a facility designated by the sponsor.

Concentrations of glucagon will be assayed using a validated liquid chromatography with tandem mass spectrometry (LC/MS) method.

Concentrations of DPC will be assayed using a validated liquid chromatography with tandem mass spectrometry (LC/MS) method. Analyses of samples collected from patients who received IMG are not planned.

Bioanalytical samples collected to measure investigational product concentrations will be retained for a maximum of 1 year following last patient visit for the study.

9.7. Pharmacodynamics

At times specified in the Schedule of Activities (see Section 2), venous blood samples will be collected and used to determine the PG concentration. The samples will be stored for up to a maximum of 1 year after the last patient visit for the study at a facility selected by the sponsor.

Samples used to assess the secondary objective endpoints will be processed within 1 year following last patient visit. Any samples remaining after 1 year will be destroyed.

9.7.1. Exploratory Sample Assessments and Storage

Collection of samples for exploratory research is also part of this study. Blood samples will be collected as specified in the Schedule of Activities (see Section 2). Samples collected and stored for exploratory analysis may be used for immunogenicity assessments.

Samples will be retained for a maximum of 15 years after the last patient visit, or for a shorter period if local regulations and ERBs allow, at a facility selected by the sponsor. The duration allows the sponsor to respond to future regulatory requests related to the NG (LY900018). Any samples remaining after 15 years will be destroyed.

9.8. Genetics

A blood sample will be collected for pharmacogenetic analysis as specified in the Schedule of Activities (see Section 2), where local regulations allow.

Samples will not be used to conduct unspecified disease or population genetic research either now or in the future. Samples will be used to investigate variable exposure or response to glucagon nasal powder (LY900018) and to investigate genetic variants thought to play a role in diabetes mellitus and related complications. Assessment of variable response may include evaluation of AEs or differences in efficacy.

All samples will be coded with the patient number. These samples and any data generated can be linked back to the patient only by the investigative site personnel.

Samples will be retained for a maximum of 15 years after the last patient visit, or for a shorter period if local regulations and/or ERBs/IRBs impose shorter time limits, for the study at a facility selected by Lilly or its designee. This retention period enables use of new technologies, response to regulatory questions, and investigation of variable response that may not be observed until later in the development of glucagon nasal powder (LY900018) or after glucagon nasal powder (LY900018) is commercially available.

Molecular technologies are expected to improve during the 15-year storage period and therefore cannot be specifically named. However, existing approaches include whole genome or exome sequencing, genome-wide association studies, multiplex assays, and candidate gene studies. Regardless of technology utilized, data generated will be used only for the specific research scope described in this section.

9.9. Biomarkers

Not applicable.

9.10. Health Economics

Not applicable.

10. Statistical Considerations and Data Analysis

10.1. Sample Size Determination

Assuming a 5% dropout rate, the study will enroll approximately 70 patients to have 66 patients completing both treatment visits with evaluable primary outcome.

A total of 66 patients are required in the study in order to achieve the primary objective with at least 90% power under the following assumptions:

- A treatment success rate of 98% for both treatments
- A noninferiority margin of 10%
- One-sided alpha level of 0.025
- A within-patient correlation of zero between 2 treatment visits

10.2. Populations for Analyses

10.2.1. Study Participant Disposition

Proportion of patients discontinued from the study and the reasons for discontinuation will be summarized by treatment group for all randomized patients.

10.2.2. Study Participant Characteristics

The patients' baseline characteristics and demographics will be obtained at entry and will be summarized for all randomized patients.

10.2.3. Treatment Compliance

No specific study data will be collected for analysis of treatment compliance.

10.3. Statistical Analyses

Statistical analysis of this study will be the responsibility of Eli Lilly and Company or its designee.

Any change to the data analysis methods described in the protocol will require an amendment ONLY if it changes a principal feature of the protocol. Any other change to the data analysis methods described in the protocol, and the justification for making the change, will be described in the statistical analysis plan (SAP) and/or in the clinical study report.

All data will be entered, verified, and archived at a contract research organization (CRO) external to Lilly and/or at Lilly. Data listings, summaries, and analyses will be performed by a CRO and/or by Lilly under the guidance and approval of statisticians at Lilly.

Unless otherwise specified, efficacy analyses will be conducted on all randomized patients who received at least 1 dose of the study drug and have evaluable efficacy outcome.

Pharmacokinetic/pharmacodynamic analyses will be conducted on data from all randomized patients who receive at least 1 dose of the study drug and have evaluable PK/PD.

Safety analyses will be conducted for all randomized patients who receive at least 1 dose of the study drug, whether or not they completed all protocol requirements (see Section 10.3.2.1).

All analyses will be based on the treatment patients actually received (if different from assigned treatment). Unless otherwise specified, all tests of statistical significance for treatment comparisons will be evaluated at a nominal level of 0.05 using 2-tailed test procedures, and confidence intervals (CIs) will be computed as 2-tailed using a 95% significance level. All tests of interactions between treatment group and other covariates will be conducted as 2-sided with an alpha level of 0.10. SAS version 9.2 or higher will be used to perform the analyses.

Additional exploratory analyses of the data will be conducted as deemed appropriate. Study results may be pooled with the results of other studies for population PK analyses purposes to avoid issues with post hoc analyses and incomplete disclosures of analyses.

10.3.1. Efficacy Analyses

10.3.1.1. Primary Efficacy

The primary outcome is the treatment success, which is defined as an increase in PG to ≥ 70 mg/dL or an increase of ≥ 20 mg/dL from PG nadir within 30 minutes after receiving glucagon, without receiving additional actions to increase the PG concentration. The nadir is defined as the minimum PG concentration at the time of or within 10 minutes following glucagon administration.

The primary analysis will be a treatment group comparison of the primary outcome. The percentage of treatment successes in each treatment and the difference in percentages will be computed. A 2-sided 95% CI will be obtained from the 1-sample mean of the paired differences in primary outcome (1=outcome observed; 0=outcome not observed) across 2 treatment visits. Noninferiority of NG will be declared if the upper limit of a 2-sided 95% CI constructed on the difference in percentages (IMG – NG) is less than the noninferiority margin of 10%.

The proposed noninferiority margin of 10% has been chosen based on the previously completed Phase 3 study (Rickels et al. 2016).

Primary efficacy analysis will only include patients who complete both treatment visits with evaluable primary outcome. The following will be considered as nonevaluable primary efficacy outcome and excluded from the analysis related to primary efficacy outcome:

- Patients with at least 1 treatment visit in which the lowest PG concentration at the time of or within 10 minutes following glucagon administration is ≥ 70 mg/dL;
- Patients receive an external measure to raise PG concentration either before glucagon administration or within the first 10 minutes of glucagon administration.

Plasma glucose concentrations assessed through a central laboratory will be used to assess treatment success. If a central laboratory measurement is missing, the SuperGL (or equivalent)

measurement from that time point will be used in general with the following additional provisions:

- Out-of-window blood draws (blood draws taken before/after the midpoint between consecutive planned measurements) that occur prior to the 30-minute time point will be included.
- Central laboratory PG concentrations and SuperGL (or equivalent) concentrations at the 30-minute time point that are measured more than 35 minutes after administration of glucagon will be considered missing.
- If a PG concentration is missing for both central laboratory and SuperGL (or equivalent) measurements, the missing value will be imputed using linear interpolation of central laboratory values.

Additional analysis will be performed if deemed necessary. The details will be provided in the SAP.

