Abbreviations: AE = adverse event; AUC = area under the concentration versus time curve; BGmax = maximal blood glucose; Cmax = maximal concentration; PD = pharmacodynamics; PK = pharmacokinetics; T1DM = type 1 diabetes mellitus; Tmax = time to maximal concentration.

Summary of Study Design:

Study I8R-MC-IGBI is a multicenter, randomized, open-label, 2-treatment, 2-period, crossover study conducted in adult patients with T1DM.

Treatment Arms and Planned Duration for an Individual Patient:

LY900018: Single 3-mg dose; nasal administration by study site personnel

GlucaGen® (Novo Nordisk A/S): Single 1-mg dose; IM injection

Number of Patients:

Approximately 70 patients with T1DM will be enrolled in order to have 66 patients complete both treatment visits with evaluable primary outcome.

Statistical Analysis: A total of 66 patients are required in the study in order to achieve the primary objective with at least 90% power using the following assumptions:

- A treatment success rate of 98% for both treatments
- A noninferiority margin of 10%
- One-sided alpha level of 0.025
- A within-patient correlation of zero between 2 treatment visits

The primary analysis will be a treatment comparison of the percentage of patients who achieve treatment success. The percentage of patients who achieve treatment success within each treatment arm and the difference in the percentages between 2 treatment arms will be computed. A 2-sided 95% confidence interval (CI) will be obtained from the 1-sample mean of the paired differences in outcome (1=outcome observed; 0=outcome not observed) across 2 study visits. Noninferiority of nasal glucagon (NG) will be declared if the upper limit of the 2-sided 95% CI constructed on the difference in percentage (IM glucagon – NG) is less than the noninferiority margin of 10%.

2. Schedule of Activities

Study Schedule Protocol I8R-MC-IGBI

Procedure	Screening Visit	Period 1 and Period 2 CRU Visits	Follow-up (or ED) Visit	Comments
	Up to 28 days before Period 1	Day 1	28(\pm 2) days after last dose of study drug	
Sign informed consent form	X			Written informed consent has to be provided before any trial-related activity and may be obtained during a separate informed consent visit to the site
Medical history	X			
Clarke Hypoglycemia Awareness Survey	X			See Appendix 8 .
Height	X			
Weight	X	X	X	During Periods 1 and 2, body weight will be collected before the start of the procedure to induce hypoglycemia

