Patients fully recovered from hypoglycemia without additional actions to increase glucose level. Specifically, in Study IGBC, at 30 minutes after glucagon dosing, 98.7% (74 out of 75 patients) of NG and 100% (75 out of 75) of intra-muscular glucagon (IMG)-treated patients achieved treatment success (defined as an increase in PG to ≥ 70 mg/dL or an increase of ≥ 20 mg/dL from nadir). The nadir is defined as the minimum glucose measurement at the time of or within 10 minutes following glucagon administration. The NG-treated patients who did not meet the above criteria did achieve both PG ≥ 70 mg/dL and an increase of ≥ 20 mg/dL from nadir at 40 minutes after dosing. Furthermore, the mean time to treatment success was 16 minutes in the NG treatment arm and 13 minutes in the IMG treatment arm (Rickels et al. 2016).

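### The planned primary interval (plain mean of paired 0/1 differences) does not hold the stated one-sided 2.5% error: at IMG success of 98–100% the true rate at the 10-point margin is about 5–9%

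*Protocol*

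**What the plan says.** Section 10.3.1.1 scores each patient 1 or 0 on each treatment and states: "A 2-sided 95% CI will be obtained from the 1-sample mean of the paired differences in primary outcome". The decision rule follows: "Noninferiority of NG will be declared if the upper limit of a 2-sided 95% CI constructed on the difference in percentages" (IMG minus NG) lies below 10 points. The synopsis repeats the method; there the interval "will be obtained from the 1-sample mean of the paired differences in outcome".

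Section 10.1 bases 66 evaluable pairs and at least 90% power on a 10% margin, zero within-patient correlation, "A treatment success rate of 98% for both treatments" and "One-sided alpha level of 0.025". Section 3.2 reports that in the completed crossover study IGBC "98.7% (74 out of 75 patients) of NG and 100% (75 out of 75) of intra-muscular glucagon (IMG)-treated patients achieved treatment success".

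The protocol names no score, exact or continuity-corrected interval and gives no rule for data without discordant pairs. Section 10.3.1.1 defers only additional analyses to the SAP, so the primary interval is settled in the protocol.

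**The concern.** Only discordant pairs carry information: b pairs where IMG alone succeeds and c pairs where NG alone succeeds. At the success rates that the protocol assumes or cites, b and c will each be a handful at most. The interval estimates its standard error from that same handful. If NG failures happen to be few, the point estimate falls and the standard error falls with it. The upper limit is then most optimistic exactly when a false claim is possible. In the extreme case b = c = 0, the standard deviation is zero and the 95% interval is a single point.

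This is the study's only non-inferiority decision. Section 5.4 gives its purpose as bridging the planned commercial product to the clinical trial product. The error rate matters precisely for the case where the commercial product does not perform as its predecessor did.

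**Working it through.** **Inputs.** n = 66 pairs, margin 0.10, one-sided alpha 0.025, success 98% on both treatments and correlation zero (Section 10.1); interval and decision rule (Section 10.3.1.1); 74/75 and 75/75 in study IGBC (Section 3.2).

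**The plan's own figure.** With independent visits, each discordant probability is 0.98 × 0.02 = 0.0196, so the variance of a paired difference is 0.0392.
- Standard error: √(0.0392/66) = 0.0244.
- Power by normal approximation: Φ(0.10/0.0244 − 1.96) = 98.4%.
- Exact power with the planned interval: 96.3%.

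The claim of at least 90% power is met, and 66/0.95 gives 70 enrolled. The plain formula needs only 42 pairs: 0.0392 × (1.960 + 1.282)²/0.10² = 41.2.

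**The planned upper limit.**
U = (b − c)/n + t(0.975, n − 1) × √(s²/n), where s² = [b + c − (b − c)²/n]/(n − 1).

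For b = 3, c = 0: s² = (3 − 9/66)/65 = 0.0441, and U = 0.0455 + 1.997 × √(0.0441/66) = 0.097.

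| b (c = 0) | Planned upper limit | Planned decision | Tango score decision |
|---|---|---|---|
| 0 | 0.0% | pass | pass |
| 1 | 4.5% | pass | pass |
| 2 | 7.3% | pass | fail |
| 3 | 9.7% | pass | fail |
| 4 | 12.0% | fail | fail |

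For comparison, the exact (Clopper-Pearson) upper limits for 2/66 and 3/66 are 10.5% and 12.7%.

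**Error at the margin.** With IMG at 100% and NG at 90%, c is always 0 and b is Binomial(66, 0.10). The planned rule passes when b ≤ 3, with probability 9.3%. Tango passes when b ≤ 1, with probability 0.8%. For other IMG rates, (b, c) was enumerated under the multinomial with NG 10 points lower and independent visits:

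| IMG / NG | Planned, n = 66 | Tango, n = 66 | Planned, n = 70 |
|---|---|---|---|
| 100 / 90 | 9.3% | 0.8% | 7.1% |
| 99 / 89 | 6.4% | 1.3% | 5.5% |
| 98 / 88 | 4.9% | 1.6% | 4.7% |
| 97 / 87 | 4.1% | 1.8% | 4.1% |
| 95 / 85 | 3.5% | 2.2% | 3.4% |

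A simulation of 400,000 draws at n = 66 gave 9.3%, 6.4%, 4.9% and 3.5% at IMG 100%, 99%, 98% and 95%. The protocol does not say whether t or z is used; at 66 pairs the two agree to within 0.1 point. Newcombe's paired interval gives 0.8%, 1.7%, 2.1% and 2.3% at IMG 100%, 99%, 98% and 95%.

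**Correlation.** If NG never succeeds where IMG fails, then c = 0 and the planned error is 9.3% at 66 pairs whatever the IMG rate. Positive within-patient correlation moves towards that case.

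**Zero width.** P(b = c = 0) at n = 66:
- 98% / 98%: (1 − 2 × 0.98 × 0.02)^66 = 7.1%
- 99% / 99%: (1 − 2 × 0.99 × 0.01)^66 = 27%
- study IGBC rates: (74/75)^66 = 41%

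**The case against.** The arithmetic is not in dispute; the weight given to it can be.

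- **Zero width changes no decision.** With no discordant pairs of 66, the Tango upper limit is 5.5% and the exact bound is 5.4%, both well below 10%. This stands: zero width is a reporting defect, and the error inflation comes only from accepting results such as two or three IMG-only successes.
- **The inflation is conditional.** The 9.3% needs IMG at 100% or nested failures, and exactly 66 pairs. It is 4.9% at the planning rate for IMG, 3.5% at 95%, and somewhat lower at 70 pairs. At a true 15-point deficit it is only 0.4–0.7% (IMG 98–100%). These limits are correct, but no case computed at the margin is at or below 2.5%.
- **The context is reassuring.** This is a Phase 1 study supplementing a manufacturing bridge, and the prior data put NG near 99%, far from the 88–90% at which the error is evaluated. That bears on how likely harm is. It does not rescue the stated alpha, which is defined at the margin.
- **The remedy costs power.** This stands. Tango at 66 pairs has 81% power at 98%/98% and about 79% at IMG 100%/NG 98.7%, where the planned interval has 99%. Bonett-Price also leaves the error above nominal, at 2.9–4.0% over IMG 95–100%, so it is only a partial repair.

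**Conclusion.** The concern holds. With 66 pairs and independent visits, the prespecified interval has a one-sided error of 4.9% to 9.3% at the 10-point margin for IMG success between 98% and 100%, the range that the protocol assumes or cites. That is about two to four times the stated 2.5%. The exact size depends on the IMG rate, the correlation and the final number of pairs: 3.5% at IMG 95%, and 4.7–7.1% at 70 pairs for IMG 98–100%.

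The practical consequence is specific. With no NG-only successes, two or three IMG-only successes out of 66 pass under the plan and fail under a Tango score or exact interval. Part of the planned interval's 96% power comes from this excess error. If NG truly performs as in study IGBC, the conclusion will probably be the same, but the trial cannot claim the error control that it states. Because this is the sole non-inferiority rule, it should be corrected before outcome data are seen.

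**What to change.** In Section 10.3.1.1 and the synopsis, replace the one-sample-mean interval with a named score-based interval for a paired difference in proportions: Tango, or Newcombe's paired hybrid score. Keep the 10% margin and the upper-limit rule. Both methods give a proper interval when there are no discordant pairs.

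Restate Section 10.1 for the chosen method. The wording change is small, but the sample-size consequence is not:

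| Interval | Power, 66 pairs, 98%/98% | Error at margin, 66 pairs, IMG 95–100% |
|---|---|---|
| Planned | 96% | 3.5–9.3% |
| Tango | 81% | 0.8–2.2% |
| Newcombe paired | 83% | 0.8–2.3% |
| Bonett-Price | 93% | 2.9–4.0% |

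At 70 pairs, Tango has 89% power and Newcombe 88%. The asymptotic score formula needs about 82 pairs for 90%: (1.960 × √0.1096 + 1.282 × √0.0392)²/0.10² = 81.4. At 99%/99%, Tango already has 91% with 66 pairs. The sponsor must either add pairs or state a lower power.

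If the number of patients cannot change, the Bonett-Price adjusted Wald interval is the smallest step. It removes the zero width and keeps power above 90%. The protocol should then say openly that the error can still reach about 4%.

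Section 10.3 requires an amendment when a principal feature of the protocol changes, and the primary interval should be treated as one.
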